## Feasibility and Acceptability Measures

Feasibility and acceptability will be assessed using session attendance (recorded as a continuous variable ranging from 1 to 4 study sessions) and retention (coded as a dichotomous

variable with participants who complete the 24-week session characterized as completers and those not attending the final session as non-completers). The Helping Relationships subscale of the Processes of Change Questionnaire will be used to examine satisfaction with PNs in the active condition. CSQ-8 will be used to compare treatment satisfaction by condition.

Efficacy Measures: The main outcome analyses and effect size estimates will be based upon biochemically verified 7-day point-prevalence abstinence at 4-, 12-, and 24-week follow-ups. Pointprevalence abstinence will be verified by saliva cotinine radioimmune assay analysis (cutoff value of < 15 ng/ml) for stated abstinence of 7 days or longer in those not currently using NRT or other nicotinecontaining products. Self-report will always be overridden by objective verification of abstinence in the final analyses. Timeline Followback (TLFB) will be used to assess Quitline contact, enrollment in smokefree.gov, prescription receipt for cessation pharmacotherapy, quit attempts (defined as a 24hour period of no smoking), and continuous abstinence. Breath samples for CO will be obtained at each study visit.

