#### Data Analysis Plan

Assessments will be designed as scannable forms for use with the Cardiff Teleform Scanner System®. Data will be verified, checked, and uploaded to an SPSS file to conduct analyses. Initial data analysis will include studies of randomization effects (group differences), distribution properties of dependent and other variables, and correlations among outcome measures.

Sample Size and Power Considerations. Our primary objective will be to examine preliminary effect sizes for PNSS-S, rather than to determine statistical significance between groups at certain p values. At the same time, we are well aware of the dangers of relying exclusively on small-scale pilots to determine the promise of novel treatment approaches. These effect size estimates have a large standard error, and we primarily will be hoping to find a pattern of results that is supportive of the experimental treatment. Effect size estimates will include odds ratios for smoking abstinence. We believe a sample size of 72 should allow adequate examination of PNSS-S intervention effect sizes while staying within the scope of a developmental project. We recognize that only medium to large effect sizes will be likely to attain statistical significance with a sample of this size. Our data also will allow us to obtain stability estimates for point-prevalence abstinence (i.e., intercorrelations among outcomes at 4, 12, and 24 weeks). Using a program that allows us to specify proportions at each time point and the correlations between time points, we will be able to get a good estimate of the sample size needed to find a significant main effect of treatment in a repeated measures analysis using generalized estimating equations. All analyses will include sex as a covariate and follow-up analyses will test the Sex x Condition interaction to determine whether sex moderates the effects.

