Treatment Feasibility, Acceptability, & Efficacy. Individual analyses of variance will be conducted to compare treatments (PNSS-S vs. SC) on the continuous variables of number of sessions attended and client satisfaction scores. For treatment retention rate (dichotomous), a chi-square analysis will be used. Analyses will test the hypothesis that PNSS-S improves point prevalence abstinence relative to SC. Tests of the effect of treatment condition on Quitline usage, quit attempts, and on 7-day point-prevalence abstinence across the 4, 12, and 24 week assessments will be conducted using GEE, which provides appropriate modeling of covariance structures when observations are correlated across time. The primary, between groups, independent variable in the GEE analysis is treatment condition assignment, which will be dummy-coded using SC as the reference group.

Following the intention-to-treat principle, all participants who have been randomized will be included in the analyses.

Potential Mechanisms of PNSS-S Effects. Sample size in this trial precludes formal mediation analysis with adequate power. The analyses are designed to test the plausibility of potential mechanisms of the PNSS-S treatment effect. We will examine change in these variables using multilevel modeling as increased social support and self-efficacy for quitting are important outcomes in and of themselves, which may affect long-term smoking outcomes and will be useful in demonstrating the longer-term effects of PNSS-S. Mediators will be examined separately, rather than simultaneously, given our limited sample size. For each mediator, we will fit a multilevel model to obtain both an initial value (intercept) and rate of change (slope) in each of these variables from baseline to week 4. We will first test whether treatment condition predicts change in these variables. We will then enter the intercept and slope parameters from these models into the main GEE model of smoking outcome to determine whether change in these variables predicts smoking outcomes. We will be able to examine whether the effect of treatment is reduced when the mediator is added to the model and can test for significance (not expected given the sample size) using the products of coefficients method. Social support in the 4 weeks after quitting also will be examined as a potential mediator of PNSS-S effects.

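### In the exploratory mediator-outcome step, week-4 abstinence does not follow the baseline-to-week-4 mediator change, so that odds ratio is partly concurrent (minor; cheap to improve)

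*Combined protocol and SAP*

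**What the plan says.** All of this is in the Data Analysis Plan unless another section is named.

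- **Mediator.** For each candidate mediator a multilevel model will "obtain both an initial value (intercept) and rate of change (slope) in each of these variables from baseline to week 4". The plan first tests whether treatment condition predicts that change.
- **Mediator-outcome step.** The plan will then "enter the intercept and slope parameters from these models into the main GEE model of smoking outcome", to see whether mediator change predicts smoking outcome. It will look at whether the treatment effect shrinks and may apply a product-of-coefficients test, for which it does not expect significance.
- **Outcome times.** The GEE tests cover "Quitline usage, quit attempts, and on 7-day point-prevalence abstinence across the 4, 12, and 24 week assessments". The efficacy measures rest on "biochemically verified 7-day point-prevalence abstinence at 4-, 12-, and 24-week follow-ups".
- **Second mediator.** "Social support in the 4 weeks after quitting also will be examined as a potential mediator of PNSS-S effects".
- **Status.** "The analyses are designed to test the plausibility of potential mechanisms of the PNSS-S treatment effect". The plan concedes that the sample is too small for an adequately powered mediation analysis.

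No section lags the outcome in this step, leaves week 4 out of it, or adjusts it for quitting that occurred before the mediator was read.

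**The concern.** A variable offered as a mechanism should change before the outcome it is meant to explain. Here one of the three outcomes lies inside the mediator's own window. If people who have already stopped smoking report more support or more confidence because they stopped, the model will show that mediator change predicts abstinence even when the mediator does nothing.

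The protocol makes this feedback possible. The nurse session falls within a week of baseline (Enrollment), and a quit date can be set there. In the PNSS-S arm a quit can prompt a quit-day call, and the weekly calls follow the stage of the quit attempt (PNSS-S condition section). Participants are told to count navigator support when they rate support for quitting (Mechanisms of PNSS-S Effect).

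The plan's caveats concern power. Low power widens an interval but does not shift the estimate, whereas feedback of this kind does shift it, and a larger sample does not remove the shift. At stake is the reading of one exploratory odds ratio: a mechanism could look more, or less, plausible than it is.

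**Working it through.** **1. Timing**

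| Quantity | Period covered | Source section |
|---|---|---|
| Mediator change | Baseline to week 4 | Data Analysis Plan |
| First outcome in the GEE | 7 days before the week-4 visit | Data Analysis Plan; efficacy measures |
| When measures are completed | At the study session | Assessments |
| Earliest planned quit-date discussion | Within one week of baseline | Enrollment; PNSS-S condition |

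The week-4 outcome window falls wholly inside the mediator window. Only weeks 12 and 24 come after it.

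**2. Inputs.** From the documents: 36 per arm (2 x 36 = 72), sex as a covariate, and a GEE over three visits. The plan gives no abstinence rates, mediator SD, correlation between visits or feedback size, so there is no figure of its own to reproduce. Those inputs are assumed below.

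**3. Simulation.** Abstinence was 10% vs 20% or 15% vs 30%, with a week 4-12 correlation of about 0.25 or 0.5. The mediator had no true effect on abstinence. Week-4 mediator = 0.5 x baseline + noise + feedback x week-4 abstinence. The model was a logistic GEE with exchangeable correlation and robust SE, with arm, sex, visit, baseline mediator and mediator change as covariates. There were 2,000 trials per setting. The true odds ratio is 1, and ranges run across the four settings.

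| Model, feedback 0.5 SD | Median log OR per SD | Median OR | p<0.05 |
|---|---|---|---|
| Planned, weeks 4, 12, 24 | 0.32-0.46 | 1.4-1.6 | 24-38% |
| Weeks 12, 24, unadjusted | 0.15-0.35 | 1.2-1.4 | 10-22% |
| Weeks 12, 24, adjusted for week-4 abstinence | 0.01-0.02 | 1.0 | 6-9% |

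With no feedback, all three models reject in 6-9%. The planned model rejects in 13-19% at 0.3 SD and 46-72% at 0.8 SD. If quitting lowers the score by 0.3 SD, the planned OR is 0.76-0.83, so the direction depends on the sign of the feedback.

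A second simulation (10% vs 25%, latent correlation 0.6, 300 trials, 0.5 SD) gave ORs of 1.32, 1.20 and 1.02 for the three models, with p<0.05 in 26%, 10% and 8%. At 400 per arm (60 trials) the planned OR was still 1.30, with p<0.05 in 97%.

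**4. Other results from the same step, at 0.5 SD feedback**

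- Arm effect on mediator change that arises through quitting alone: (0.20 - 0.10) x 0.5 = 0.05 SD, or (0.30 - 0.15) x 0.5 = 0.075 SD. Both are small, so the product stays small.
- Product-of-coefficients test: about 0-1% false positives, or 6-14% if PNSS-S is also assumed to raise the mediator by 0.5 SD directly.
- Reduction in the treatment log OR when the mediator is added: median -1% to 3%.

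**5. Feedback through earlier quit attempts.** If any 24-hour attempt by week 4 (assumed in 45-60% of participants) raises the score by 0.5 SD, the planned OR is 1.2-1.5 (19-27%). The adjusted week 12 and 24 OR is 1.1-1.3 (9-13%), so some bias remains.

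**6. What the later-outcome models lose.** Detection of a real effect (log OR 0.5 / 0.8 per SD, no feedback):

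| Effect acts on | Planned | Weeks 12, 24 unadjusted | Weeks 12, 24 adjusted |
|---|---|---|---|
| Quitting by week 4 only | 21% / 44% | 13% / 22% | 8% / 6% |
| Weeks 12 and 24 only | 18% / 38% | 28% / 54% | 29% / 57% |
| All visits | 34% / 64% | 28% / 54% | 21% / 40% |

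Expected abstinent visits: 36 x (0.10 + 0.20) = 10.8 or 36 x (0.15 + 0.30) = 16.2 per visit. Over three visits that is 32.4 or 48.6; over weeks 12 and 24 it is 21.6 or 32.4.

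**7. Post-quit support.** This variable has no value for people who do not quit, and it follows the quit by definition, so it cannot explain the initial quit. It can precede abstinence after the four-week period, but the plan neither names that outcome nor says how non-quitters are handled.

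**The case against.** The strongest reply is that the step is exploratory and carries little weight. The plan limits it to plausibility and states: "Our primary objective will be to examine preliminary effect sizes for PNSS-S, rather than to determine statistical significance". Rejection rates at p<0.05 therefore describe a decision the plan does not rely on. This stands as a limit on severity. It does not answer the shift in the estimate itself, which the caveats do not mention.

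Several stronger readings are tempting, and the documents do not support them.

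- **False mediation.** A reader might take 24-38% as the risk of declaring mediation. That figure is for the single mediator-outcome coefficient; the product test the plan names is far less affected.
- **Planning input.** A reader might infer that the future trial will be sized on this odds ratio. The Methodology section promises the effect of PNSS-S on mechanisms, which is arm to mediator, and the sample size text uses abstinence proportions and their correlations over time.
- **Post-quit support always misordered.** Sustained and continuous abstinence are among the measured outcomes, and for later abstinence the order could be correct. The gap is that the plan does not specify it.
- **Always upward.** The support scale covers negative as well as positive support, so the sign is not fixed.
- **Model not estimable.** A reader might infer that two readings cannot support an intercept and slope. The assessment schedule is an attachment not shown and the model form is unstated, so this cannot be concluded.

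It is also fair that the simulations have no missing data, whereas the plan counts missing as smoking, and that they use observed change in place of estimated slopes. Replacing the planned model would be a trade-off, as the last table shows, which argues for adding analyses beside it.

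**Conclusion.** The point holds as a minor, inexpensive improvement confined to the exploratory mediator-outcome step. The week-4 outcome does not follow the mediator, and early quitting that changes support or self-efficacy scores can bias the mediator-outcome odds ratio. That timing follows from the text. The size rests entirely on assumed rates, correlations and feedback: roughly OR 1.4-1.6 where the truth is 1, if quitting raises the score by 0.5 SD, and below 1 if it lowers it.

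A reader might infer that the trial's main result is at risk. It is not: the primary abstinence comparison does not contain the mediator, the arm effect on mediators (Aim 2) does not use this step, and the check on reduction of the treatment effect barely moves.

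**What to change.** Change wording in the plan only; all data are already collected.

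- Keep the planned model, but describe its mediator-outcome odds ratio as a partly concurrent association.
- Beside it, report the odds ratio with its interval for week 12 and 24 outcomes only, once without and once with adjustment for week-4 abstinence.
- Base any statement on plausibility of a mechanism on the pattern across the three versions, and say that none of them establishes mechanism.
- Analyse post-quit support only as a descriptive predictor of later abstinence among those who quit.

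The plan should state the costs:

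- Fewer events: about 22-32 expected abstinent visits under the assumed rates, for 5-6 covariates.
- Without adjustment, some feedback bias remains.
- With adjustment, a mechanism acting through quitting by week 4 is removed, so a null adjusted result does not rule it out.
- Some bias through earlier quit attempts can remain even after adjustment.
- The post-quit support analysis rests on few people: about 11-16 expected week-4 abstainers of 72 under the assumed rates.

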## **Missing Data**

We will explore patterns of missing data to determine possible mechanisms of missingness and will explore different techniques to impute missing data values in different analyses. In the primary analyses using GEE, we will include all participants and will assume that participants with missing data are smoking.

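### If the abstinence GEE uses a logit link, checking whether the treatment effect shrinks once the mediator is added will usually understate mediation (minor)

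*Combined protocol and SAP*

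**What the plan says.** All references are to the combined protocol and SAP.

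- **Data Analysis Plan, Potential Mechanisms of PNSS-S Effects.** Each mediator is modelled from baseline to week 4 with a multilevel model that yields an initial value (intercept) and a rate of change (slope). The steps then are:
  1. "We will first test whether treatment condition predicts change in these variables".
  2. "We will then enter the intercept and slope parameters from these models into the main GEE model of smoking outcome", to see whether change in the mediator predicts smoking.
  3. "We will be able to examine whether the effect of treatment is reduced when the mediator is added to the model".
  4. In the same sentence as step 3, the team "can test for significance (not expected given the sample size) using the products of coefficients method".
- **Status of the analysis, same paragraph.** "Sample size in this trial precludes formal mediation analysis with adequate power", and "The analyses are designed to test the plausibility of potential mechanisms of the PNSS-S treatment effect".
- **Sample Size and Power Considerations.** "Effect size estimates will include odds ratios for smoking abstinence". No link function is named for the GEE anywhere.
- **Missing Data.** "In the primary analyses using GEE, we will include all participants and will assume that participants with missing data are smoking".

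**The concern.** Step 3 compares the treatment coefficient from two models, one without the mediator terms and one with them. On a linear scale, in a randomised comparison, the difference would equal the indirect effect. On the log-odds scale it does not. Adding any variable that predicts abstinence moves the treatment coefficient away from zero, even when treatment has no effect on that variable. The observed change is therefore the mediated part minus a scale artefact.

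The plan adds two such variables. The slope can carry mediation. The intercept is a pre-treatment value and cannot, so if it predicts abstinence it contributes artefact only.

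At stake is how the mechanisms in Aim 2 are described when the pilot is used to plan the full-scale trial. The caveat about sample size concerns noise. It does not cover a systematic shift.

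**Working it through.** **Plan's own figure.** There is none to reproduce. The plan gives no abstinence rates, mediator effects or link function. All inputs below are assumptions except the 36 per arm.

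**Model.** T is treatment (0 or 1) and M is mediator change, normal with SD 1 and mean a·T. Then logit P(abstinent) = b0 + c'·T + b·M. The values b0 and c' are solved by numerical integration so that averaging over M gives the assumed abstinence in each arm.

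- Total effect: logit(p1) − logit(p0).
- Apparent share mediated: (total − c') / total.
- Share mediated on the log-odds scale: [logit(p1) − logit(q)] / total, where q is PNSS-S abstinence if M kept its SC distribution.
- Share of the risk difference mediated: (p1 − q) / (p1 − p0).

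**Base case: SC 10%, PNSS-S 22%, a = 0.3, b = 1.0.**

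- Total = 0.932 (OR 2.54).
- c' = 0.754 (OR 2.13).
- Apparent share = (0.932 − 0.754) / 0.932 = 19%.
- q = 0.1786. Log-odds share = 0.260 / 0.932 = 28%.
- Share of the risk difference = 0.0414 / 0.12 = 34.5%. The like-for-like contrast is 19% against 28%, because 34.5% is on another scale.
- Product of coefficients = 0.3 × 1.0 = 0.300, on the conditional log-odds scale.

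**Size of the artefact.** With a = 0 and the same rates, nothing is mediated, yet the OR rises from 2.54 to 2.87 (log OR 1.054). In this model c' = 1.054 − a·b, so the observed fall is a·b − 0.123 (0.300 − 0.123 = 0.177). The artefact depends on b and the rates but not on a. The fall therefore vanishes when a·b is at or below 0.123, that is, when a is about 0.12 SD or less at b = 1.0.

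**Other single-mediator cases.**

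| SC / PNSS-S | a | b | OR without → with mediator | Apparent fall | Log-odds share |
|---|---|---|---|---|---|
| 5% / 11% | 0.5 | 0.7 | 2.35 → 1.71 | 37% | 39% |
| 10% / 22% | 0.5 | 0.7 | 2.54 → 1.90 | 31% | 35% |
| 10% / 22% | 0.8 | 0.7 | 2.54 → 1.54 | 54% | 56% |
| 10% / 22% | 0.3 | 1.5 | 2.54 → 2.11 | 20% | 37% |
| 20% / 44% | 0.3 | 1.5 | 3.14 → 3.08 | 2% | 28% |
| 20% / 44% | 0.2 | 1.0 | 3.14 → 3.18 | rise | 15% |

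**Adding the baseline intercept** (SD 1, assumed independent of the slope; marginal OR 3; a = 0.3; slope effect 0.7):

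- SC 10%, no intercept term: OR 3.00 → 2.62, log-odds share 18%.
- SC 10%, intercept effect 1.1: OR 3.00 → 3.12, a rise, with 15% mediated on the log-odds scale and 20% of the risk difference.
- SC 20%, intercept effect 0.7: OR 3.00 → 2.97, with 16% mediated on the log-odds scale.

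**Against sampling noise.** Five mediated scenarios were simulated with 36 per arm, three correlated visits, an exchangeable logistic GEE and 400 trials each. The gap between a·b and the coefficient change was 0.04 to 0.24 log-odds. The SD of the estimated change was 0.17 to 0.29. No reduction was seen in 3% to 13% of trials, from noise and bias together.

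**The case against.** **The shrinkage check does not decide mediation.** A reader might infer from the first half of the sentence that mediation is judged by a falling odds ratio. The documents do not support that. The same sentence names the product of coefficients as the significance test, and that product does not compare treatment coefficients across models. No threshold is attached to the reduction. This objection stands. The point concerns one of two checks, though the plan expects no significance from the other, so the descriptive one may carry weight.

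**No mechanism would be dropped.** A reader might infer that a true mechanism would be abandoned. No such rule exists. The plan regards support and self-efficacy as worthwhile outcomes in themselves, and Aim 2's comparison of the arms on mechanisms is untouched.

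**The two models need not use different people.** A reader might infer that missing week-4 mediator values remove participants from one model. A multilevel model can give predicted values to participants with baseline data only, so this does not follow, although the plan does not say how such cases are handled.

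**The bias is often small.** This stands at low abstinence with a moderate or large shift in the mediator. With one mediator term, the OR fell in every case of a grid with SC 5% to 40%, OR 2 or 3, a 0.3 to 0.8 and b 0.4 to 1.1. In the strongest-mediator cases the change slightly exceeded the marginal indirect effect (0.812 against 0.804). With full mediation the adjusted OR goes to 1 and nothing is hidden. That grid, however, leaves out the baseline intercept that the plan also enters.

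**The analysis is exploratory.** This is true, and the simulated gap stayed below the sampling SD within each scenario. It lowers the severity but does not remove the bias.

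**Conclusion.** The point holds as a minor one. If the link is logit, which is inferred from the odds ratios and not stated, the check on whether the treatment effect shrinks is biased and usually understates mediation. Under assumed inputs the understatement runs from a few percentage points (31% against 35%) to a substantial part of the effect (19% against 28%; 2% against 28% with a very strong mediator and higher abstinence). No fall, or a rise, despite real mediation occurs mainly with a small treatment effect on the mediator, higher abstinence or a strongly prognostic intercept. It would be too strong to say that the plan generally hides mediation. The product of coefficients is not affected by the cross-model comparison.

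**What to change.** Change a few sentences in the Potential Mechanisms paragraph:

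- Name the GEE link.
- Keep the product of coefficients as the main mediation estimate, with a bootstrap interval.
- Replace the shrinkage comparison with an indirect effect on the risk-difference scale. Use the fitted outcome and mediator models, standardise predicted abstinence over each arm's mediator distribution, and give a bootstrap interval that resamples participants.
- If models with and without the mediator are still shown, put the baseline intercept in both, fit both on the same participants, and state that the change in odds ratio is not the share mediated.

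The cost is a short script. No new data are needed and the primary analysis does not change. There are two downsides. With about 4 and 8 abstainers per visit (36 × 0.10 = 3.6 and 36 × 0.22 = 7.9 under the assumed rates), bootstrap intervals will be wide and may be unstable. The estimate also still assumes no unmeasured confounding of mediator and outcome, as the planned approach does.

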The primary objective of this project is to examine the feasibility, acceptability and initial efficacy of a peer navigation social support for smoking cessation (PNSS-S) intervention for HIV-positive smokers. We will enroll 78 HIV-positive smokers, regardless of their readiness to quit, into a 24-week randomized pilot study to determine whether enhanced treatment (using a PN to navigate smoking cessation, help obtain medication and treatment, improve adherence to treatment, and provide social support for quitting) will increase quit attempts and smoking cessation rates (measured by 7-day point prevalence) compared with standard care (SC; provider recommendation to quit and quit line referral using the 5A's).

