## Methodology

We will adapt an existing, highly effective PN training program that was developed by Co-I [name] to increase engagement in care within the HIV clinic. The PNs for smoking cessation will be former daily smokers who quit smoking and have remained smoke-free for at least two years. We will train the two PNs, enroll 6 HIV-positive smokers to test the intervention, and finalize our protocol. We will refine the PNSS-S based on feedback from the PNs, the 6 participants, and the study nurse. Next, we will conduct a pilot RCT (N = 72) to test the feasibility, acceptability, and initial efficacy of PNSS-S in a randomized, 2-group, repeated measures design. We will randomize 36 HIV-positive smokers to each condition: PNSS-S or standard care (SC). Assessments will be collected at baseline (BL), and at 4-, 12-, and 24-weeks following BL. We will examine the effect of PN on Quitline contact, quit attempts, adherence to pharmacotherapy, smoking cessation rates, 7-day point prevalence abstinence (with biochemical verification), sustained abstinence, self-efficacy for quitting, social support for smoking cessation, study retention and satisfaction. We will calculate a preliminary effect size estimate of PNSS-S on smoking and other secondary outcomes and mechanisms of change. Data will be used to plan a future full-scale RCT.

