# **Pharmacotherapy**

Participants who set a quit date during the study period will be prescribed one of four FDAapproved options by their treating MD and medication will be provided through their insurance plan and usual pharmacy: 1) Nicotine replacement therapy (NRT) prescribed as an 8-week course of treatment with transdermal nicotine patch - initial dose starting at 21 mg for 4 weeks (14 mg for those smoking 5-10 cigarettes per day); 2) combination NRT in the form of patch/lozenge or patch/gum; 3) varenicline; or 4) bupropion.

Participants will select treatment, based on the advice of their physician. Dose and duration of the oral medications will be at the discretion of the physician (consistent with clinical care).

See Appendix for medication coverage list by insurance plan in RI.

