## **Assessments**

All measures will be completed by paper and pencil at the study session. The measures have a participant ID and a study session number as the only identifiers (See Attachments).

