## Mechanisms of PNSS-S Effect

Social support for quitting will be assessed using the Partner Interaction Questionnaire, which assesses negative and positive support for quitting. Participants will be instructed to include all forms of support for quitting (including PN support if assigned to the PNSS-S condition). Self-efficacy for smoking cessation will be measured using the Contemplation Ladder, a one-item Likert-type scale (rating 1-10). In participants who set a quit date, adherence to pharmacotherapy will be measured via participant self-report and pharmacy refill report at each study session.

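### The added mediator, social support in the 4 weeks after quitting, has no value for participants who never quit, so testing it as a mediator of the PNSS-S effect conditions on a post-randomisation event (minor)

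*Combined protocol and SAP*

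**What the plan says.** Under Potential Mechanisms of PNSS-S Effects, the Data Analysis Plan models each mediator by its starting value and slope from baseline to week 4. It then enters these into the main GEE for abstinence and looks at whether the treatment effect shrinks. It closes with a separate item: "Social support in the 4 weeks after quitting also will be examined as a potential mediator of PNSS-S effects". Neither the quit that starts the 4 weeks nor the visit that supplies the score is defined, and nothing is said about participants who do not quit.

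Four other places bear on this:

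- **Instrument** (Mechanisms of PNSS-S Effect): "Social support for quitting will be assessed using the Partner Interaction Questionnaire, which assesses negative and positive support for quitting". No look-back period is given.
- **Timing** (Methodology; Assessments): "Assessments will be collected at baseline (BL), and at 4-, 12-, and 24-weeks following BL", and "All measures will be completed by paper and pencil at the study session". The text describes no visit tied to the quit date.
- **Who is enrolled** (Description and Purpose of the Project): "We will enroll 78 HIV-positive smokers, regardless of their readiness to quit". Under Pharmacotherapy and the two condition descriptions, setting a quit date is optional and may come at any time in the study.
- **Quit attempts** (Efficacy Measures): an attempt is 24 hours without smoking, recorded by Timeline Followback (TLFB).

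**The concern.** A mediator of a randomised comparison needs a value in every randomised participant, or a rule for those without one. Here the value starts to exist only when a participant quits. Getting smokers to quit is what PNSS-S is for, so the people with a value are selected by an event that the assigned arm may influence. Quitters on PNSS-S may include people who would not have quit under standard care. Support could then differ between arms, or fail to differ, through selection alone.

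The planned comparison adds a second difficulty. The treatment effect without the mediator can be estimated in all 72. With the mediator it can be estimated only in those scored, unless values are invented for non-quitters. A fall in the coefficient may then reflect a different sample and not a mechanism. Mechanisms are the second specific aim, and the pilot is meant to inform a full-scale trial, so a result of this kind could be read as support for a mechanism it does not test.

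**Working it through.** **Plan's own figure.** The plan gives no number of expected quitters or of participants scorable on this mediator, so there is nothing to reproduce beyond the sample size: 36 × 2 = 72 randomised, and 6 + 72 = 78 enrolled. Both agree with the text.

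**Step 1: non-quitters.** This needs no assumed number. A participant with no quit has no 4 weeks after quitting. However quits are timed, the variable is absent for this group. It is undefined for them, not merely missing.

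**Step 2: quitters with a visit in the window.** Take visits at weeks 4, 12 and 24 (Methodology). A quit at week q has a visit in the next 4 weeks if q lies in weeks 0–4, 8–12 or 20–24. Quits in weeks 4–8 or 12–20 have none. The documents give no distribution of quit dates, so the timings below are assumptions, with one quit per person.

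| Assumed quit dates | Share with a visit within 4 weeks |
|---|---|
| Uniform, weeks 0–24 | (4 + 4 + 4)/24 = 50% |
| Uniform, weeks 1–24 | (3 + 4 + 4)/23 = 48% |
| Uniform, weeks 4–24 | (4 + 4)/20 = 40% |
| Uniform, weeks 1–12 | (3 + 4)/11 = 64% |
| Exponential from week 1, cut at week 24, mean 8 / 4 / 2 weeks | 54% / 65% / 80% (simulated) |
| All in weeks 1–4 | 100% |
| All in weeks 4–8 | 0% |

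With k independent, uniformly timed attempts per person, the share with at least one covered attempt is 1 − 0.5^k: 50%, 75% and 88% for k = 1, 2 and 3.

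**Step 3: number scorable.** n = 72 × share ever quitting × coverage. The share ever quitting is not in the documents; 20% to 60% is assumed.

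- Coverage 50%: 72 × 0.20 × 0.50 = 7 to 72 × 0.60 × 0.50 = 22.
- Coverage 100%: 72 × 0.20 = 14 to 72 × 0.60 = 43.

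Even at full coverage, everyone who does not quit stays outside the analysis.

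**Step 4: can selection alone produce a difference?** An illustration with assumed parameters: log-odds of quitting = −0.4 + 0.9 × arm + 1.0 × motivation, with motivation standard normal. Support = 0.6 × motivation + 0.8 × noise, with no effect of arm. Simulated quit rates are 42% (SC) and 60% (PNSS-S). Mean support among quitters is 0.29 and 0.20, a difference of about 0.09 SD, lower on PNSS-S, with no true effect.

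For scale, the standard error of an arm difference with n scorable participants split equally is about 2/√n SD: 2/√7 = 0.76 and 2/√43 = 0.30. The illustrated bias is thus 0.09/0.76 = 12% to 0.09/0.30 = 30% of one standard error. It shows that bias can arise. It does not estimate how large the bias will be here.

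**The case against.** The strongest reply is that this is one exploratory item in a pilot that already calls mediation underpowered and aims only at plausibility. The illustrated bias is small against sampling error, and the inputs the plan names for sizing the next trial are abstinence proportions and their correlations, not this variable. All of that stands and limits the importance of the point. It does not remove it: low power concerns precision, whereas an undefined variable and a sample selected by quitting concern what is being estimated.

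Four stronger readings are tempting, and the documents do not support them.

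- **That about half of quitters are lost.** This needs a single quit per person spread evenly over 24 weeks. The nurse visit within a week of baseline raises the quit date, so early quits, which the week-4 visit would catch, are plausible. Repeat attempts also raise coverage.
- **That quitters between visits cannot be scored.** The questionnaire's look-back is not stated, and the schedule of assessments is an attachment not available here. A retrospective report paired with a TLFB-dated quit might fill this gap. It would not help non-quitters.
- **That post-quit support cannot be a mechanism at all.** The outcome is 7-day abstinence at three visits, and the navigator's role includes helping people maintain or regain abstinence. Support after a first quit could affect later abstinence. The valid objection is to the selected sample and to attributing the overall effect to this variable.
- **That the plan contradicts its statement that "all participants who have been randomized will be included in the analyses".** That sentence closes the efficacy text, before the mechanisms heading. Missing Data ties the inclusion of everyone to the primary GEE and allows other techniques elsewhere. The mechanisms text gives no analysis set for this mediator, which is a gap and not a clear contradiction.

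**Conclusion.** The point holds in a limited form, as a minor issue. From the text alone, the variable is undefined for participants who never quit, and testing it as a mediator of the overall PNSS-S effect on abstinence conditions on quitting. Any fall in the treatment effect when it is added could come from the change of sample. How many quitters also lack a measurement depends on quit timing, the number of attempts and the look-back, none of which the documents give. The size of any bias is likewise unknown. The primary GEE and the baseline-to-week-4 mediator models do not depend on quitting and are unaffected.

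**What to change.** In Potential Mechanisms of PNSS-S Effects, stop treating this variable as a mediator and replace the sentence with wording such as: *Social support after quitting will be summarised descriptively by arm among participants with a TLFB-dated quit and a study visit within the following 4 weeks. The number scorable in each arm will be given, and no mediation claim will be made. Mediation analyses of social support will use the visits anchored to randomisation and scheduled for all 72 randomised participants.* The sentence should also say whether the first dated quit or any dated quit counts.

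This costs one passage of analysis-plan text and no new data. The downside is that the question of support after quitting becomes descriptive only.
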